20.1.12.1 Frequency table of potentially clinically important values Percentages for the PCI tables will be calculated as: 2. Summary by visit for all subjects: % subjects with PCI values at visit x (total) = # subjects with a post – baseline PCI value at visit x # subjects with a post – baseline assessment at visit x *100 4. Summary overall post baseline for all subjects: % subjects with PCI values (total) = # subjects with at least 1 post – baseline PCI value # subjects with at least 1 post – baseline assessment *100	
Ordering of parameters
 
Laboratory parameters, vital signs and ECG parameters will be ordered alphabetically within their parameter group (e.g., hematology, clinical chemistry, and urinalysis). Visits will be sorted chronologically. If changes from BL are displayed by visit all visits will be displayed first followed by all the changes from baseline.
 
Not exact values
 
Not exact laboratory values such as < x, > x will not be included in the analysis of continuous parameters. The frequency of occurrence of not exact values will be displayed in the respective table where applicable.
 
Categorical parameters
 
For categorical parameters, 2 types of tables are created:
 
 Frequency tables display the pre-defined categories by visit and overall post-baseline. Shift tables display the shift from baseline at each visit and overall. 
Both types of tables show the number of subjects still in the trial (n) at the visit and the number of missing values (nMiss) at the visit. For the overall presentation, all post-baseline values on treatment are taken into account and nMiss is the number of subjects without any on-treatment post-baseline values.
 
In tables where parameters are classified as abnormal low, normal, abnormal high based on reference ranges, and alert low, normal, alert high based on sponsor-defined alert ranges the available pre-defined categories must be displayed in tables even if there are categories to which no subjects belong. Categories that are not

Formerly read:	Now reads:
	applicable must be omitted.
Original Section 20.1.11.9: Confidence intervals for difference in incidence rates	
	Section with programming specifications for the confidence intervals for difference in incidence rates deleted, as no confidence intervals for incidence rates will not be presented.
Section 18.1.12.1: Overall post-baseline value (original Section 20.1.10.2)	
Therefore, all post-baseline assessments, including unscheduled assessments, are taken into account and the “worst” of those will be considered. “Worst” for the different parameters is defined as follows: PCI xxx > PCI yyy: PCI xxx is worse than PCI yyy, and in case both PCI xxx and PCI yyy for the corresponding parameter is observed post baseline during the respective period of interest (treatment period, Tapentadol Period, Observation Period), PCI xxx will be counted for this parameter.	Therefore, all post-baseline assessments, including unscheduled assessments, are taken into account. For the overall post-baseline summary subjects might have both low and high values. These subjects will be categorized in a new category “high and low” and excluded from the categories “high” and “low”. The inclusion of this category in the frequency and shift tables is only required if there are any subjects falling into this category.
Original Section 20.1.11: Modified constipation assessment scale	
The answer to each item will be entered in the eCRF. The eCRF will calculate the total score as sum of the individual answers. Thus the total score will be available in the SDTM data set. If at least one answer is missing or at least one answer is “Unable to Assess”, the eCRF will assign the total score to “Unable to Assess”.	Section deleted.
Original Section 20.1.13: Interim analysis – Algorithm to determine actual CP_{min}	
	Section deleted.
Section 18.2: Sponsor defined alert ranges for laboratory parameters (original Section 20.2)	
Table 12: Potentially clinically important values for laboratory parameters	Potentially clinically important values for laboratory parameters are assessed based on the sponsor defined alert ranges, and can be both, either alert high or alert low values. The sponsor defined alert ranges were defined in the laboratory statement of work and are implemented in the SDTM data. Therefore, they are not repeated here.

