5.2 Sample size

The sample size was estimated to reject the null hypothesis of the inferiority of tapentadol PR to morphine PR when comparing responders evaluated at the end of the 14-day Treatment Period (Part 1, i.e., the primary endpoint). The percentage of responders in both treatment arms is estimated to be 80% based on data from previous trials and extrapolation to the trial population under investigation. The non-inferiority margin is set to a difference of 20% for the primary endpoint (i.e., responder rate, see Section 13.1).

To show the non-inferiority of tapentadol PR compared to morphine PR using a Farrington Manning (1990) test by a non-inferiority margin of 20% with at least 80% power and a 1-sided significance level of alpha = 0.1, 69 subjects are required in the FAS, assuming a 2:1 randomization of tapentadol PR:morphine PR.

A one-sided alpha of 0.1 is considered appropriate based on a method proposed by Hlavin et al. (2016). The approach makes use of prior knowledge and the concept of extrapolation from a larger population to a small target population (i.e., pediatric population), to reduce the burden of evidence in pediatrics by relaxing the Type I error, while controlling a certain posterior belief, i.e., confidence after successful pediatric trials, in effectiveness of the drug in children.

Further details for the application of the concept of Hlavin et al. (2016) in the context of this trial are provided in a separate document that is available upon request.

The periodic reviews of the Data Monitoring Committee (DMC) (see Section 6.3) during the trial address only safety and no efficacy data and thus have no impact on the sample size.

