- As time to discontinuation refers to discontinuation from *treatment*, it was specified that the dates of first and last IMP intakes should be used for the respective calculations rather than the dates of the scheduled visits.
- The protocol specifies that subjects should have taken their last IMP of the Treatment Period on the day of VE or the evening before. In reality; this intake might have occurred earlier, in particular for subjects that discontinued treatment. For the derivation of the primary endpoint, it was therefore specified that the last 3 days of treatment should be considered for pain assessment rather than the last 3 days prior to VE.
- The options of the multiple imputation were specified more clearly, covering how the imputation by treatment group should be done, which variables to be included in the model and how to handle the different pain scales and the ranges of their respective scores.
- The prior distribution for the precision of the random effects used in the Bayesian analysis of the primary endpoint was redefined based on the expert recommendation provided in the literature (Gelman 2016).
- The factor for the morphine PR equivalent of tapentadol PR that has to be used for some calculations was added.
- A specification of days to be considered for the SOWS (Day 0 = day of last IMP) was added, as deviating from trial day definition.
- For the Z-score related to *weight* and *height*, a rule to derive the age in months based on the available information in years was provided as required for the calculation.

7.2.2 Amendment 01

Amendment 01 to the final SAP was prepared to cover the following topics:

- Changes arising from protocol Amendment 02 dated 23 June 2015 and protocol Amendment 04 dated 23 May 2017 were implemented, including the following major changes:
 - The update of the alpha for the primary endpoint analysis based on the methodology proposed by Hlavin et al. (2016) with the consequence of sample size reduction and use of 80% confidence interval for the primary endpoint analysis.
 - The deletion of the interim analysis for the sample size reassessment due to the sample size reduction. The adaptive 2-stage design of the trial has been simplified to a fixed 1-stage design.

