9.4 Full Analysis Set

The Full Analysis Set includes all allocated and treated subjects, i.e., all allocated subjects who were administered any amount of IMP.

The FAS is the primary analysis set, i.e., the analysis set used for the conduct of the primary analysis of this trial.

The analysis on the FAS will be conducted according to the allocated treatment.

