13 EFFICACY ANALYSES

13.1 Primary endpoint

The primary efficacy endpoint and its analyses only involve Part 1 of the trial.

The primary efficacy endpoint is a binary variable “responder”. A subject is defined as “responder” if both of the following criteria are met:

- Completion of the 14-day Treatment Period. A definition is given in Section [8.2.2](#).
- One of the following calculated from the scheduled pain assessments (“pain right now”) is documented during the last 3 days of treatment in the Treatment Period:
 - Average pain <50 on a VAS for subjects aged 12 years to less than 18 years; or <5 on the FPS-R for subjects aged 6 years to less than 12 years.
 - Average reduction from baseline of pain ≥ 20 on a VAS for subjects aged 12 years to less than 18 years; or ≥ 2 on the FPS-R for subjects aged 6 years to less than 12 years.

Pain assessments during the last 3 days of treatment in the Treatment Period means the last six scheduled pain assessments up to the time point of last IMP intake of the Treatment Period whether these fall across 3 (morning assessment 2 days before last IMP intake until evening assessment at the day of last IMP intake given last IMP taken in the evening) or 4 calendar days (evening assessment 3 days before last IMP intake until morning assessment at the day of last IMP intake given last IMP taken in the morning).

Summary statistics for the primary efficacy endpoint for the FAS and PPS will be provided.

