
Handling missing data
 
...
 
Information on the pain assessments during the last 3 days of the Treatment Period might only be partially available. In this case Multiple Imputation will be used to impute missing values:
 
1. For each treatment group, a multivariate normal distribution for the vector of the last 6 scheduled pain measurements during the Treatment Period, denoted by (Y_1, \dots, Y_6), is assumed $(Y_1, \dots, Y_6) \sim MVN(\mu, \Sigma)$. Missing observations are assumed to depend on the observed values of the subjects in the same treatment group. Therefore, in both treatment arms, missing pain assessments will be imputed using information from an imputation model that is only based on the subjects in the respective arm, with baseline pain intensity, age group and underlying pain condition as explanatory variables. The multiple imputations will be done via SAS PROC MI. The imputation model will be based on the default Markov chain Monte Carlo (MCMC) method for general patterns of missingness (Dmitrienko et al. 2005).
 
For the sake of reproducibility of the results, the seed for pseudo-random number generation will be set to 550366 for each of both treatment arms.
 
The number K of imputed data sets will be set to 200, resulting in 200 complete data sets:
 
 Number of imputed data sets: $K = 200$ 	
Handling missing data
 
...
 
Information on the pain assessments during the last 3 days of treatment in the Treatment Period might only be partially available. In this case Multiple Imputation will be used to impute missing values:
 
1. For each treatment group, a multivariate normal distribution for the vector of the age group (AGE), underlying pain condition (PAIN) and baseline pain intensity (BASE) as well as the last 6 scheduled pain measurements during treatment of the Treatment Period, denoted by (Y_1, \dots, Y_6), is assumed $(AGE, PAIN, BASE, Y_1, \dots, Y_6) \sim MVN(\mu, \Sigma)$. Missing observations are assumed to depend on the observed values of the subjects in the same treatment group. Therefore, in both treatment arms, missing pain assessments will be imputed using information from an imputation model that is only based on the subjects in the respective arm. The multiple imputation will be performed once for all subjects using VAS, and once for all subjects using FPS-R. To ensure that the imputed values are within the range of the respective pain scale (0-10 for FPS-R and 0-100 for VAS), minimum and maximum values for the variable to be imputed should be specified.
 
The multiple imputations will be done via SAS PROC MI. The imputation model will be based on the default Markov chain Monte Carlo (MCMC) method for general patterns of missingness (Dmitrienko et al. 2005). A BY statement will be

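### The primary multiple imputation leaves out completion status, so completers' missing pain scores are drawn partly from early stoppers' scores; the likely bias is small and the correction is cheap.

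*SAP*

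**What the plan says.** The primary analysis set is the FAS, which SAP 9.4 defines as "all allocated subjects who were administered any amount of IMP". It therefore includes children who stop early. A responder must complete the 14 days and also meet a pain criterion (SAP 13.1). SAP 13.1.1 says that completion will be known for every child, while the pain scores may be incomplete and are then multiply imputed.

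The scores are "the last six scheduled pain assessments up to the time point of last IMP intake of the Treatment Period" (SAP 13.1). SAP 7.2.1 explains that Amendment 02 made this change because discontinued children take their last dose earlier: "the last 3 days of treatment should be considered for pain assessment rather than the last 3 days prior to VE".

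The imputation rule is in SAP 18.1.8.2 (the same sentence appears in the amendment table of 17.1): "missing pain assessments will be imputed using information from an imputation model that is only based on the subjects in the respective arm". PROC MI runs once per pain scale for all children, with treatment as the only BY variable and under a missing-at-random assumption. The variables are age group, pain condition, baseline pain and the six scores. Completion status, time on treatment and reason for stopping are not among them.

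**The concern.** A child who does not complete is a non-responder whatever pain score is imputed. The imputed six scores therefore reach the primary result only through completers. Yet a completer's missing scores, from about the last three days of a 14-day course, are drawn from a distribution that also contains the scores of children just before they stopped. If stoppers' pain differs from completers' pain given age group, pain condition and baseline, the imputed values for completers move toward the stoppers.

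The direction is not fixed. Protocol Table 1 provides for stopping for lack of efficacy, which would raise imputed pain and lower imputed response. It also provides for stopping because an opioid is no longer needed, which would do the opposite. The difference between arms is affected only if the dropout share, the stoppers' pain or the amount of missing data differs between them.

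**Working it through.** **The plan's own figure.** SAP 5.2 gives: "The percentage of responders in both treatment arms is estimated to be 80"%; "The non-inferiority margin is set to a difference of 20% for the primary endpoint"; "assuming a 2:1 randomization of tapentadol PR:morphine PR"; and "with at least 80% power and a 1-sided significance level of alpha = 0.1, 69 subjects are required in the FAS". With 46:23 and the Farrington-Manning formulas of 18.1.8.2, exact binomial enumeration gives 80.8% power, against 78.5% at 44:22. So 69 reproduces, and it does not change with the point made here.

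**Inputs that the documents do not give.** There is no Part 1 dropout rate, missing-score rate or pain level of stoppers. SAP 7.2.2 only describes Part 1 discontinuation as very low. All of these are assumptions below.

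**Shift in the imputed score.** Let d be the dropout share and D the mean pain of stoppers minus that of completers, given the covariates. With no score observed, the pooled model centres a completer's imputed score at d x D above the completer mean. With k scores observed, the average shift is

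d x D x [1 - k b / (a + (k - 1) b)], where a = s² + c, b = r s² + c, c = d(1 - d)D².

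Assume s = 22 VAS points, r = 0.6 and D = 20.

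- d = 5%: c = 19, a = 503, b = 309.4. The shift is 0.05 x 20 = 1.0 point with no score observed. With three observed it is 1.0 x [1 - 928.2/1121.8] = 0.17.
- d = 20%: c = 64, a = 548, b = 354.4. The shift is 4.0 points with none observed, 1.4 with one and 0.62 with three.
- d = 30%: 6.0 points with none observed and 0.88 with three.

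The sign reverses for D = -20.

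**Shift in an arm's responder rate.** Assume completers' mean VAS 38, between-child SD 18, within-child SD 10, baseline 55 (SD 20) and correlation 0.4. A responder has a six-score mean below 50 or a fall of at least 20. A completer then responds with probability 79.3%. For completers missing all six scores:

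arm bias = (1 - d) x share of completers missing all six x (imputed minus true response probability).

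| Dropout, stoppers' mean VAS | Response imputed by SAP model | Bias, 10% missing all six | Bias, 20% missing all six |
|---|---|---|---|
| 5%, 65 | 76.0% | -0.32 points | -0.64 points |
| 15%, 65 | 69.9% | -0.8 | -1.6 |
| 25%, 65 | 64.4% | -1.1 | -2.2 |
| 5%, 20 | 80.2% | +0.08 | +0.16 |
| 15%, 20 | 81.9% | +0.2 | +0.4 |

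First row: 0.95 x 0.10 x (76.0 - 79.3) = -0.3; simulation of the 20% case gives -0.6 to -0.7. With completion status in the model, the imputed response returns to about 79% in every row. If 20% of completers have three of six scores observed instead, the bias is at most about 0.1 point, even at 25% dropout.

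A separate simulation of full data augmentation in one arm (SD 22, correlation 0.6, stoppers 25 points higher) compared the pooled model with completers only. The responder rate moved by -0.3 points at 5% dropout, -0.4 at 10%, and -1.2 to -1.3 at 20%. With no difference in pain, the change was within simulation error.

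**The case against.** The strongest objection is size. The SAP describes Part 1 discontinuation as very low, so the 15% and 25% rows are not what the sponsor expects. They also sit badly with the planning rate of 80%: at 25% dropout no arm can exceed 75%, and here it would be 0.75 x 79.3% = 59%. Nor does any document suggest that 10-20% of completers will lack all six scores. Protocol 12.8 provides for regular diary checks and counts a child as compliant with 80% of entries. The standard error of the difference at 46:23 and 80% is √(0.16/46 + 0.16/23) = 10.2 points, so a bias of 0.3 to 0.7 is under 0.1 of it. All of this stands. One qualification is that 80% of 28 twice-daily entries still allows five gaps, so a compliant completer could lack most of the last six scores.

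It can also be said that sensitivity analysis 3 already removes the imputation. It does, but it counts a completer with no score as a non-responder. If 10% of completers had none, that alone would lower the arm by 0.95 x 0.10 x 79.3 = 7.5 points, which would swamp an effect of 0.3. It therefore cannot isolate this one. No planned analysis imputes within completers or conditions on completion.

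A reader might infer that, because the trial is open-label, the arms will probably lose children for opposite reasons, and might add the extremes: 2.2 + 0.4 = 2.6 points in the difference. The documents do not support that. They say nothing about how reasons will differ by arm, and similar dropout in both arms would largely cancel.

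**Conclusion.** The omission is real and follows from the current text of SAP 13.1, 13.1.1 and 18.1.8.2. It produces a systematic pull whenever stoppers' scores differ from completers' given the model's covariates. It is minor. At 5% dropout the bias in one arm's responder rate is about -0.3 to -0.7 points if stoppers are in high pain (mean 65), or +0.1 to +0.2 if in low pain (mean 20), and that already assumes 10-20% of completers miss all six scores. It reaches about -2 points only at 25% dropout with 20% missing all six, and it is close to zero when about half the scores are present. These sizes rest on assumed pain levels, dropout and missingness.

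A reader might conclude that the flaw could overturn the non-inferiority result. Nothing in the documents or the working supports this: the effect is small against a 20-point margin, and it enters the difference only to the extent that the arms differ. The case for changing the plan is that this is the primary analysis, the bias is avoidable and no planned analysis addresses it.

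**What to change.** In SAP 18.1.8.2, impute missing values of the six scores from a model fitted to treatment completers within each arm. Keep the existing all-subject model only to impute missing baseline pain for non-completers, because the logistic regression still needs it. Alternatively, add the fully observed completion indicator to the imputation vector, to be dropped in an arm where every child completes. If the primary rule is to stay, prespecify one of these as a sensitivity analysis.

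The cost is a sentence or two in the SAP and a small programming change. The downside lies in the morphine arm of about 23 children: slightly fewer children in the imputation model, or one more variable that may rest on one or two non-completers. Fitting to completers avoids the second problem and does not depend on whether any child stops.

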18 APPENDIX

18.1 Programming specifications

18.1.1 Introduction

The purpose of this section is to give technical details for SAP text implemented as Statistical Analysis System (SAS) code.

18.1.2 General specifications

18.1.2.1 Percentages and decimal places

If not otherwise specified, the following rules are applied:

- Study Data Tabulation Model (SDTM) or Analysis Data Model ADaM data sets will contain unrounded values.
- For presentations, the following rounding rules apply:
 - Percentages are presented to 1 decimal point.
 - Percentages equal to 0 or 100 are presented as such without a decimal point.
 - For descriptive summary statistics, the same number of decimal places as in the raw data are presented when reporting minimum and maximum values, 1 more decimal place when reporting mean, median, quartiles and confidence interval (CI) and standard deviation (SD).
 - P-values are presented to 4 decimal points.
 - Ratios are presented to 3 decimal points.

The above described displaying rules must not be changed (e.g., rounding) for the ICTR text and are used 1:1 in the body report as well.

18.1.2.2 Presentation of descriptive statistics

Calculation of mean: if not otherwise specified (e.g., for pharmacokinetic data), the arithmetic mean is used.

Table 11: Presentation of descriptive statistics in clinical trials

Number of non-missing values	n	missing n	mean	SD	min	Q1	median	Q3	max
0	+	+	-	-	-	-	-	-	-
1.2.3.4	+	+	+	-	+	-	+	-	+
≥5	+	+	+	+	+	+	+	+	+

+ summary statistic will be presented; - summary statistic will not be presented.

n = number of values, SD = standard deviation, min = minimum, Q1 = first quartile, Q3 = third quartile, max=maximum

18.1.2.3 Presentation of differences and changes

For differences between active and active comparator, active will constitute the minuend and comparator the subtrahend.

For changes from baseline, the baseline value will constitute the subtrahend and the later value the minuend.

18.1.2.4 Trial day count

The day of first IMP intake is defined as trial Day 1.

Calculate the trial day according to the following rules:

- If date < trial Day 1 then trial day = Date – trial Day 1.
- If date ≥ trial Day 1 then trial day = Date – trial Day 1 + 1.

